Aim 1 (Strategy 1): Modulating the limbic system as an approach to treatment: mPFC iTBS. Cigarette smokers will be randomized to receive 10 days of real iTBS or sham iTBS directed to the mPFC. Intermittently the desire to smoke, cigarette value using behavioral economic demand, preference for immediate gratification (delay discounting), and cigarette self-administration will be assessed. Smoking cue-evoked brain activity will also be measured when individuals are asked to 'crave' (passive limbic engagement) versus 'resist' the craving (executive engagement)(7,11-13). We hypothesize that iTBS will: 1) decrease the behavioral smoking measures described above, which will be explained by a selective 2) decrease in the neural response to cues when individuals 'allow' themselves to crave, and 3) sustain these changes over a time period sufficient to overcome the initial quit attempt (~7-14 days).

Aim 2 (Strategy 2): Modulating the executive system as an approach to treatment: dlPFC iTBS. Aim 2 will follow the design of Aim 1. The procedures will be identical, except iTBS will be delivered to the left dlPFC. We hypothesize that iTBS will: 1) decrease the behavioral smoking measures described above, which will be explained by a selective 2) increase in the neural response to cues when individuals attempt to 'resist' the cues, and again 3) sustain these changes over a similar period as specified in Aim 1.

Exploratory Aim- Evaluate baseline frontal striatal connectivity and discounting rate as factors to predict an individual's likelihood of responding to Strategy 1 versus Strategy 2. We will test the hypotheses that individuals with a higher ratio of (mPFC-striatal)/(dIPFC-striatal) connectivity will be more likely to have a behavioral change after Strategy 1. Various demographics (e.g. gender, smoking history, socioeconomic status, subclinical depressive symptoms, self-efficacy, & motivation to quit will be evaluated as explanatory variables.

The outcomes of the present aims will resolve a critical gap in our knowledge regarding the relative efficacy of 2 promising TMS treatment strategies. These outcomes will be directly translated to a larger longitudinal study evaluating a multipronged approach to improving outcomes in traditional pharmacotherapy or behavioral treatments.

Methods and Measures

Design

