The long term goal of the research is to develop non-invasive brain stimulation as an evidence-based tool to facilitate abstinence during the first week after a quit attempt, as this is a robust predictor of 6-month treatment outcomes with traditional pharmacotherapeutic and behavioral interventions. The next step in pursuit of that goal is to systematically and parametrically evaluate the efficacy of two promising TMS treatment strategies (LTP-like stimulation to the mPFC (Aim 1), LTP-like stimulation to the dIPFC (Aim 2)) as tools to change smoking behavior and brain reactivity to smoking cues. These aims will be addressed in serial (Aim 1 Years 1-3, Aim 2 Years 3-5). A randomized, double-blind, sham-controlled design will be used for each aim. In total, 138 smokers will be recruited from the tri-county area surrounding Winston-Salem, NC. Current cigarette smokers seeking to quit smoking and willing to set a quit date will be recruited from the tri-county area using digital and print advertising in diverse media outlets. Following informed consent and screening, participants will be randomized to receive real or sham TMS to the mPFC (Aim 1, Years 1-3) or the dlPFC (Aim 2, Years 3-5) (see Table 1 and TMS Procedures below for more details regarding sham controls and double blinding procedure). During the Treatment Phase, participants will receive 10 sequential days of TMS (with additional behavioral and MRI scanning (see Table 1). Participants will receive TMS at least 3 times a week for a total of 10 TMS sessions. During the follow-up phase, participants will receive 4 maintenance TMS sessions once a week for 4 weeks. During the Follow Up Phase, behavioral assessments will be acquired weekly for the first 4 weeks (see Table 2), and daily EMA will be acquired. Consistent with the CNDS model, the primary hypotheses are that LTP-like stimulation to the mPFC and LTP-like stimulation to the dlPFC will both lead to a decrease in

smoking cue-reactivity in the salience network (neuroimaging outcome), and cigarette value (behavioral outcome) but that directly targeting the value circuit (mPFC) will be more efficacious. Additionally, we will test the hypothesis that individuals with higher discounting rates and cigarette valuation at baseline will respond more to the stimulation strategies compared to those with lower baseline discounting and valuation (Exploratory Aim).

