Hypothesis Aim 1: Based on the framework predicted by CNDS theory, and preliminary work (see Study 4), we anticipate that mPFC stimulation will lead to a decrease in brain reactivity to cues during the "allow" condition (passive limbic engagement). We will analyze the neuroimaging data in concert with the behavioral data, evaluating the hypotheses that 1) mPFC iTBS will decrease the brain reactivity to cues in the 'allow' condition (with no consistent link to the 'resist' condition) and that 2) this will be related to the behavioral change in a dose-dependent manner. This will be achieved by extracting the average BOLD signal timecourse and the percent signal change during the CIG versus NEU blocks from a priori anatomically defined regions of interest (ROIs), including the striatum (ventral striatum and dorsal striatum), insula, inferior frontal gyrus, and anterior cingulate cortex. Ventral striatal and dorsal striatal ROIs are derived from the FSL Oxford-GSK-Imanova striatal atlas, mapped via probabilistic diffusion tractography (109) in agreement with anatomical projection zones from the frontal cortex (1). Hypothesis Aim 2: Based on the framework predicted by CNDS theory, and prior studies of dlPFC stimulation in smokers (4-9), we anticipate that dIPFC stimulation will lead to an increase in executive control circuitry (left dlPFC, posterior parietal cortex) during the "resist" condition (executive engagement). As in Aim 1, we will analyze the neuroimaging data in concert with the behavioral data, evaluating the hypotheses that 1) dIPFC iTBS will decrease the brain reactivity to cues in the "resist" condition (with no consistent link to the "allow" condition) and that 2) this will be related to the behavioral change in a dose-dependent manner. The ROI based outcomes of Aim 2 will be compared with the outcomes of Aim 1 using standard general linear modeling as well as a data-driven hierarchical model (see Integration below). As an experimental control, for both Aims we will also calculate the percent signal change from the primary motor cortex, a region which should not be differentially modulated by mPFC or dIPFC stimulation. Although some studies have used the visual cortex as a control region a recent meta-analysis by our group demonstrated that the visual cortex is typically activated more to drug cues than neutral cues (78). Secondary functional connectivity analysis: Additionally, an exploratory seed-based functional connectivity analysis using psychophysiological interactions (PPIs) will be performed using the TMS stimulated ROIs (mPFC and dlPFC) and the striatal target regions (ventral striatum, dorsal striatum- defined above) as seed regions. These data will be compiled across participants and compared between the mPFC and dIPFC stimulation days. Group analyses will be performed using a random effects model limiting significant clusters to those that meet p<0.05 family-wise error corrected.

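### Aim 2's imaging hypothesis carries opposite signs for the 'resist' condition, no sign is tied to a region, and no correction is stated for the region-of-interest tests

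*Combined protocol and SAP*

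**What the plan says.** The sign of the Aim 2 imaging effect is stated in three places in the combined protocol and SAP:

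- Objectives, Aim 2: dlPFC stimulation is expected to produce an "increase in the neural response to cues when individuals attempt to 'resist' the cues". No region is given.
- Outcome Measure(s), Neuroimaging Outcomes, opening sentence of Hypothesis Aim 2: dlPFC "stimulation will lead to an increase in executive control circuitry (left dlPFC, posterior parietal cortex) during the 'resist' condition". Two regions are named.
- The next sentence there, which gives the hypothesis to be evaluated: dlPFC "iTBS will decrease the brain reactivity to cues in the 'resist' condition", "with no consistent link to the 'allow' condition". No region is given.

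The Design section adds a primary hypothesis for both targets: a fall in "smoking cue-reactivity in the salience network (neuroimaging outcome), and cigarette value (behavioral outcome").

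The pre-set ROIs are listed once, under Hypothesis Aim 1, as "including the striatum (ventral striatum and dorsal striatum), insula, inferior frontal gyrus, and anterior cingulate cortex". Left dlPFC and posterior parietal cortex are not among them. The measure to be extracted is percent signal change, cigarette versus neutral blocks.

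Table 2 marks brain reactivity to smoking cues as a primary dependent measure. The Sample Size section claims 80% power at a 5% type 1 error rate for behavioral and brain measures alike. The only multiplicity statement, "limiting significant clusters to those that meet p<0.05 family-wise error corrected", closes the paragraph on the secondary, exploratory connectivity analysis.

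**The concern.** A confirmatory imaging test needs a region, a condition, a contrast and a sign. For Aim 2 the condition and contrast are given, the sign is given both ways, and the region is left open in two of the three statements. A reader of the final report could not tell from the plan whether a rise or a fall in a given region during 'resist' supports the hypothesis.

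The missing correction adds to this. With several ROIs, no primary one and no adjustment, the 5% error rate claimed in the Sample Size section does not describe the chance of at least one false positive among the imaging tests.

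Timing makes it more pressing. Under Plans for Interim Analysis of Efficacy Data, the PI receives unblinding codes at 20% increments of recruitment, starting at n=27. A sign or region settled after such a look could be chosen with group results in view.

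**Working it through.** **1. The statements side by side**

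| Place | Sign in 'resist' | Region |
|---|---|---|
| Objectives, Aim 2 | increase | none |
| Hypothesis Aim 2, opening sentence | increase | left dlPFC, posterior parietal cortex |
| Hypothesis Aim 2, hypothesis to be evaluated | decrease | none |
| Design, primary hypothesis (both targets) | decrease (condition not stated) | salience network |

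Rows 2 and 4 concern different regions and can both be true. Rows 1 and 3 conflict as written. Row 3 can be squared with row 2 only by supplying a region that the text does not give.

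**2. The plan's own power figure**

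Inputs from Sample Size and the TMS procedures: 108 usable data sets, two aims, 2:1 allocation, d = 0.8, 5% error rate (two-sided assumed, since sidedness is not stated).

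- Per aim: 108 / 2 = 54, so 36 active and 18 sham.
- d / √(1/36 + 1/18) = 0.8 / 0.2887 = 2.771.
- Power ≈ Φ(2.771 − 1.960) = Φ(0.811) = 79.1% (77.6% with the noncentral t).

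This agrees with the stated 80% for one contrast at 5%. The AR(1) repeated-measures version cannot be rebuilt because the correlations are not given. Also, 138 × 0.78 = 107.6, so 108 reflects retention alone. Taking off the stated 10% imaging loss leaves about 97 (107.64 × 0.9 = 96.9). That is about 32 versus 16 per aim, with about 74% power.

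**3. Chance of at least one false positive**

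Assume one two-sided test at 5% per ROI. The listed ROIs number five: ventral striatum, dorsal striatum, insula, inferior frontal gyrus and anterior cingulate. Adding left dlPFC and posterior parietal cortex makes seven. Under independence the chance is 1 − 0.95^m:

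- 'Resist', m = 5: 1 − 0.95^5 = 22.6%.
- 'Resist', m = 7: 1 − 0.95^7 = 30.2%.
- Both conditions, m = 14: 1 − 0.95^14 = 51.2%.

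ROIs in one brain are correlated, but the documents give no correlations. The table uses simulated, equally correlated normal statistics (400,000 draws) at assumed values:

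| Tests | Independent | Correlation 0.5 | Correlation 0.8 |
|---|---|---|---|
| 5 | 22.6% | 18.3% | 12.8% |
| 7 | 30.2% | 23.0% | 14.8% |
| 14 | 51.2% | 34.7% | 19.7% |

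If only one pre-stated sign counted (0.025 per test), independence would give 11.9% for m = 5 and 16.2% for m = 7. The plan cannot claim these lower figures while its sign is unsettled.

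**4. Cost of correcting across all ROIs instead of naming one**

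Bonferroni for 36 versus 18 at d = 0.8:

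- Seven tests, 0.05 / 7 = 0.0071: power about 53% (t: 49%).
- Fourteen tests, 0.05 / 14 = 0.0036: power about 44% (t: 40%).

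One pre-named contrast keeps the 79%.

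**The case against.** The strongest defence is regional: executive regions up, salience and limbic regions down. The Design section's salience-network decrease fits that reading and is not evidence of a contradiction. The defence works for the Design section and the opening Aim 2 sentence. It does not settle the Objectives against the hypothesis to be evaluated, since neither names a region and no sign-to-region assignment appears anywhere. The decrease sentence closely parallels the Aim 1 sentence, so a carried-over word is plausible, but the documents cannot show it.

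A second defence is that the ROI list sits under Aim 1 and is open-ended, while the two executive regions are named a few lines later under Aim 2. That stands. The fault is that the list is not closed and no ROI is primary, not that the regions are absent from the plan.

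A third is that family-wise correction is stated. It is, but at cluster level and in the connectivity paragraph. Even read broadly, it controls error within a map and does not adjust several extracted ROI means.

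A reader might infer that almost any result would count as confirmation, or that the imaging aim cannot be refuted. The documents do not support this. The hypothesis concerns one condition, expects no consistent link to 'allow', requires a dose-dependent relation to behavioral change, and has primary motor cortex as a control region. A null result, an effect only in 'allow', or no link to behavior would not fit. These limits are partial: the behavioral variable is not named, and the plan lists six primary ones (Q0, alpha, two QSU factors, two discounting magnitudes).

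**Conclusion.** The point holds. The Objectives and the hypothesis to be evaluated give opposite signs for the same target and condition. No sign is tied to a region in a way that resolves this, and no correction is stated for the ROI tests of a primary measure.

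The relevant size is the 'resist' family: 22.6% (five ROIs) to 30.2% (seven) under independence, and about 13% to 23% at assumed correlations of 0.8 to 0.5, against a claimed 5%. A reader might take 51% as the headline, but it requires 14 independent tests and counts 'allow' results, where the Aim 2 hypothesis expects no consistent effect.

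These figures assume one two-sided 5% test per ROI, the stated ROI counts, and equal correlation where correlation is used. Aim 1's sign is consistent throughout (a decrease, in 'allow' where a condition is named), so for Aim 1 only the missing primary ROI and correction apply.

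**What to change.** - Reconcile the Objectives and Hypothesis Aim 2 by stating one sign per named region for 'resist'. An executive-region increase fits the Objectives and the opening Aim 2 sentence, but the sponsor must confirm what was intended. If the decrease is meant, name its regions and amend the other statements.
- Close the ROI list for each aim. Include left dlPFC and posterior parietal cortex if the increase is intended.
- Before any unblinded look, name one confirmatory contrast per aim: a single ROI or a defined composite, cigarette versus neutral, real versus sham, in the stated condition and with its sign. Which ROI or composite to use is the sponsor's choice.
- Treat the remaining ROI and condition tests as secondary, with Holm correction, and say which analyses the cluster-level correction covers.

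The cost is SAP wording, with no new data or visits. Fewer imaging contrasts can be called confirmatory, but the one named per aim keeps the power of a single 5% test instead of the roughly 53% left after Bonferroni over seven ROIs.

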Preliminary data demonstrating the systematic Development of Non-Invasive Brain Stimulation for Addiction.

Over the last 4 years our laboratories at the Medical University of South Carolina (MUSC) and Virginia Tech Carillion Research Institute (VTCRI) have performed 3 independent studies and 1 joint study which directly contribute to the rationale and design of the present proposal. While both of our research groups have a long history of publications which have contributed to the scientific thoughts that went into this proposal, the most germane studies are summarized below:

In Study 1, we demonstrated that the frontal-striatal circuits Figure 5. In a pilot study by [name] & [name], after 5 involved in limbic drive and in executive control can be differentially activated through TMS in healthy, nonsmokers. In this study TMS was applied to a cortical node of the limbic circuit (frontal pole/vmPFC) and to the executive control circuit (dlPFC) while participants were in the MRI environment [(10) Figure 3]. Thus, demonstrating that TMS can selectively modulate limbic regions.

days of vmPFC cTBS (Strategy 1), individuals that received real TMS had a significant decrease in mPFC, insula and cingulate response to cigarette cues. This was not present in the Sham group. (Data shown are within group contrasts Visit 1 vs Visit 6, Factorial design, k = 25, voxel level p<0.05, uncorrected).

In Study 2, we demonstrated that 6 sessions of LTD-like TMS (cTBS) to the vmPFC (Strategy 1 in the present proposal) delivered in a single day caused a specific decrease in orbitofrontal cortex and ventral

striatal/accumbens BOLD signal in cocaine users (all of whom smoked cigarettes) relative to sham stimulation ([name] et al 2015). At the time, this was the first study to apply multiple doses of cTBS to the vmPFC.

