Study Visit Procedures: At all visits, individuals will provide a urine screen to detect recent use of drugs of abuse and pregnancy, a breath carbon monoxide (CO) sample to detect recent cigarette smoking, and a breath sample to test for recent alcohol use. During the consent visit, visits 1, 6, 10 and follow up visits samples will be collected to determine cotinine (nicotine metabolites) levels in the urine. Samples will be taken from the urine sample provided for the drugs of abuse screen, no additional samples will be required from the participant. At visits 1, 6, 10 and follow up visits (Assessment visits), participants will complete a battery of behavioral assessments following active TMS or sham (see Table 2). MRI scanning (at visits 1 and 10) will occur prior to TMS in order to isolate cumulative, rather than acute, effects of TMS. At all visits participants will be required to provide a CO reading at least 50% of their baseline CO measure to ensure they are at least 6 hours deprived from cigarettes. Cigarette deprivation will be use to increase craving and responding for cigarettes. Short term cigarette deprivation has known amplification effects on the brain response to smoking cues (93, 94). Moreover, we have extensive experience with successfully using this deprivation procedure (33, 41).

Table 2 1. Biochemical and self-report assessment of tobacco use and dependence						
Measure	Time (Min.)	Visits	Description			
Carbon monoxide (CO Level)	1	1-10, and follow-ups	Breath CO provides an accurate measure of recent exposure to CO , including from smoking combustible tobacco products (95). The CO measurement will be used to determine recency of smoking.			
Timeline Follow-Back (TLFB) interview	5	1, 6, 10, and follow-ups	This self-reported tobacco product use interview asks participants to retrospectively estimate the number of tobacco products they've used each day for the past 30 days or since the previous assessment, whichever is fewer (89).			
Fagerström (FTND)	3	1, 6, 10, and follow-ups	This 6-item questionnaire quickly assesses degree of cigarette dependence (96, 97). Test for Cigarette Dependence.			
2. Measures of t	tobacco pr	oduct value an	d sensitivity (**PRIMARY DEPENDENT MEASURES)			

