Questionnaire on Smoking Urges-Brief (QSU)	2	1 - 10 and follow-ups	This 10-item questionnaire assesses cigarette craving . Participants will be asked to rate from 1 (strongly disagree) to 100 (strongly agree) their agreement with several statements (e.g., "I have a desire for a cigarette right now," and "Nothing would be better than smoking a cigarette right now."). Factor analyses support two factors: one that reflects a strong desire and intention to smoke and one that reflects relief from negative affect associated with an urgent desire to smoke (45).			
Hypothetical Purchase Task (**Demand Alpha, Q0) (HPT Cigarettes)	5	1, 6, 10, and follow-ups	The hypothetical purchase task (HPT), a validated measure for cigarette demand, (98, 99) will assess cigarette purchases at various price conditions. Participants will hypothetically purchase quantities of cigarettes to use over a 24-hour period across ascending prices (e.g., \$0, 0.12, \$0.25, \$0.50, \$1.00, and \$2.00 per cigarette). The HPT has been shown to be predictive of treatment outcomes (100).			
3. Cognitive/beha	vioral tasl	k (** PRIMAR	Y DEPENDENT MEASURE)			
Delay- discounting tasks (*discounting rate, \$1K)	5	1, 6, 10, and follow-ups	Participants will be asked to choose between two conditions in which varying amounts and delays to behavioral outcomes (e.g., \$50 now or \$100 later) are presented. We will use magnitudes of \$100 and \$1000 which are the most thoroughly documented among the literature (101). Across consecutive choices, the delay to the larger outcome will be titrated until reaching the participant's indifference delay (i.e., the delay at which s/he equally values both options). This indifference delay indexes individual participants' rates of delay discounting. [61]. Monetary delay discounting has been documented to be predictive to treatment success for smokers (39).			
1. Brain Reactivity to Smoking Cues (**PRIMARY DEPENDENT MEASURE)						

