After the MRI scanning visits participants will be escorted into the Brain Stimulation Research Laboratory ([name] research suite) where scalp localization will be performed for the TMS procedure. The Cartesian position of the coil (X,Y,Z) will be determined by standardized positions from the EEG 10-20 system: 1) AFZ will be used for the mPFC stimulation (Aim 1), 2) F3 will be used for the left dlPFC stimulation (Aim 2). The angular position of the coil (pitch, yaw, roll) will be determined by the individual's cortical geography using the individual's T1 scan for guidance. The locations and coil orientation will be indicated on a nylon cap which will be worn during the TMS sessions. We will then determine the participant's resting motor threshold (RMT, the minimal amount of stimulation required over the hand area of the primary motor cortex to induce contraction of the APB muscle of the hand 50% of the time) via the standardized PEST procedure (106, 107). The procedures for acquiring the motor threshold, performing cortical localization, standardized procedures, blinding, establishing standardized paradigms and training regimens for all staff, as well as safety and ring the experimental procedures are consistent with our prior publications (7,27, 54, 63, 69, 78, 111). We will also publish a Standard Operating Procedure document and video file as supplementary material with any publications that arise from this project (as in 111, supplement).

For Aim1 (Strategy 1) stimulation will be over mPFC. For Aim 2 (Strategy 2) stimulation will be over the left dlPFC. The Aims will be pursued in serial, with a 2:1 active versus sham randomization for each Aim. Participants will receive 20 trains of stimulation (1200 pulses total; each train: 3 pulse bursts presented at 5Hz, 15 pulses/sec for 2 sec, 8 sec rest, 10 pulses/train; 110% RMT, MagPro) using a figure 8 coil (Coil Cool-B65 A/P). This is the iTBS sequence initially published (3) which has been used in clinical depression treatment (46). During each real and sham TBS session each day the amplifier output will be escalated ("ramping" in 5% increments over 30 seconds) up to 80% to 110% RMT to enhance tolerability. The time between the end of the TBS procedures and the beginning of the behavioral assessments will be compiled and used as covariates in subsequent analyses.

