Behavioral Outcomes: For the treatment phase (10 days of real/sham TBS), the primary behavioral outcomes include Cigarette demand (Q0 and alpha), Craving (QSU Intention, QSU Relief), and Delay Discounting (\$100 and \$1000). For the treatment phase the analysis will be performed using repeated measures ANOVA on change scores from baseline for each visit. The main independent variable in the ANOVA will be time (visits on day 1, 6, 10), group (real or sham) and their interaction. For correlations of observations across visits an AR(1) structure will be considered and compared with other structures such as compound symmetry and a general structure. The primary hypothesis is the interaction. If the interaction effect for an outcome is significant, we will conclude there is statistical evidence of overall treatment effect. If the spaghetti plots suggest trends (e.g., linear, quadratic, or piecewise changes) we will treat time as a continuous variable and fit repeated measures regression models along with group and its interaction with continuous time as independent variables.

Neuroimaging Outcomes: For the treatment phase, primary analysis. Image pre-processing will be conducted with FSL v. 5.0: (FMRIB Analysis Group, Oxford, UK) (108) realignment to the first volume, smoothing with an anisotropic 8-mm Gaussian kernel, high-pass filtering, resampling to 2-mm isotropic voxels, and stereotactic registration to the Montreal Neurological Institute 152-subject average template. Subjects with >3 mm movement (total mean frame displacement across the entire task) will be excluded from analysis.

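### The plan specifies no real-versus-sham test for the primary imaging outcome; the one group comparison it names for the ROI results is Aim 2 versus Aim 1, which is not randomised

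*Combined protocol and SAP*

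**What the plan says.** All references are to the combined protocol and SAP.

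- **Status of the outcome.** Table 2 lists "Brain Reactivity to Smoking Cues (PRIMARY DEPENDENT MEASURE" as a heading. Under Study Visit Procedures, "MRI scanning (at visits 1 and 10) will occur prior to TMS in order to isolate cumulative, rather than acute, effects of TMS", so each participant has two scans.
- **Randomisation.** The TMS Treatment section runs the Aims serially, "with a 2:1 active versus sham randomization for each Aim". The Design section places Aim 1 in Years 1-3 and Aim 2 in Years 3-5.
- **Behavioural analysis.** Under Outcome Measure(s), Behavioral Outcomes, the model contains time, "group (real or sham) and their interaction". The interaction is the primary hypothesis.
- **Imaging analysis.** The Neuroimaging Outcomes paragraph covers pre-processing and a motion exclusion. Hypothesis Aim 1 then predicts that "mPFC iTBS will decrease the brain reactivity to cues in the 'allow' condition", and describes extracting percent signal change for cigarette versus neutral blocks from several ROIs. Hypothesis Aim 2 says that dlPFC "stimulation will lead to an increase in executive control circuitry (left dlPFC, posterior parietal cortex") in the resist condition, and then that cue reactivity in the same condition will fall. The group comparison comes next: "The ROI based outcomes of Aim 2 will be compared with the outcomes of Aim 1 using standard general linear modeling". A motor-cortex control region follows. Sham is not mentioned in either hypothesis paragraph.
- **Power.** The Sample Size section claims 80% power at d=0.8 for behavioural and brain measures together, from 108 usable data sets.

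**The concern.** Between the two scans every participant attempts to quit, works through the same booklets and sees the same cue task again. Cue reactivity could therefore move in both arms without any effect of stimulation. Only the randomised real-versus-sham contrast separates the two explanations, and the imaging text does not name it.

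The comparison that is named does not fill the gap. Real mPFC and real dlPFC stimulation are given to cohorts enrolled in different years. A shift common to both Aims cancels in that contrast, so the contrast would not itself report the shift as a TMS effect. It also says nothing about whether sham participants changed as much.

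An analyst following the imaging section literally could report the active-arm change and the Aim comparison without ever testing the randomised contrast on a primary outcome.

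**Working it through.** **1. Is a real-versus-sham imaging test written anywhere else?** The candidates are:

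- Behavioral Outcomes: real/sham by time, but stated for behavioural outcomes only.
- Follow-up phase paragraph: contrasts between two groups, but the phases are analysed separately and both scans fall in the treatment phase.
- Exploratory Aim: a hierarchical model nested within cTBS/iTBS, not real/sham.
- Analytical Plan: a general sentence on t-tests or ANOVA between groups, with no outcome, groups or change contrast named.
- Motor-cortex control: a check of regional specificity. A cue-related shift from quitting could spare motor cortex in both arms.

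None joins ROI outcome, real versus sham, and Visit 1 to Visit 10.

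**2. Reproducing the stated power.** Method: two-sample t-test, two-sided 5%, noncentrality = d / √(1/n₁ + 1/n₂), with d=0.8.

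- Equal groups: 26 per group reach 80%. The plan's 28 per group give noncentrality 2.993 and power 83.6%.
- The plan's 108: 138 × 0.78 = 107.6. Per Aim, 46 × 0.78 = 35.9 and 23 × 0.78 = 17.9, that is 36 v 18. Noncentrality is 2.771 and power 77.6% (79.1% by the normal approximation). This is close to the stated 80%.
- The plan's own method uses four time points and an AR(1) correlation whose value is not given. It cannot be rebuilt, and it does not describe an outcome scanned twice.

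**3. Applying the 10% imaging loss.** The 108 uses retention only; 138 × 0.78 × 0.90 = 96.9. Per Aim, 46 × 0.78 × 0.90 = 32.3 and 23 × 0.78 × 0.90 = 16.1, that is 32 v 16. Noncentrality is 2.613 and power 72.5%.

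**4. Sensitivity at 32 v 16.** The documents do not say whether d=0.8 is in change-score or single-scan SDs, and give no scan-rescan correlation ρ, so ρ is an assumption here. If d is in single-scan SDs, the standardised effect is 0.8/√(2(1−ρ)) for a change score and 0.8/√(1−ρ²) after adjustment for the Visit 1 value.

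| ρ (assumed) | Change score | Adjusted for Visit 1 |
|---|---|---|
| 0.3 | 58% | 77% |
| 0.5 | 73% | 84% |
| 0.7 | 91% | 95% |

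The Interventions section says some participants will not be scanned but gives no number. If half were unscanned (an assumption; 18 v 9), power at d=0.8 in change-score SDs would be 47%.

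**5. What a within-arm reading would do.** This is an illustration, not a procedure in the plan. It uses 32 v 16, no TMS effect, and an equal fall in both arms of assumed size, with 40,000 simulated trials per row.

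| Shared fall (SD of change) | Active arm significant | Active significant, sham not | Real-versus-sham test |
|---|---|---|---|
| 0.2 | 19% | 17% | 5% |
| 0.3 | 38% | 30% | 5% |
| 0.5 | 78% | 42% | 5% |

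In a separate run with 36 per active arm, an Aim 2 versus Aim 1 comparison also rejected about 5% of the time.

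**The case against.** The strongest reply is that the sham comparison is plainly intended. The Objectives describe two double-blind, sham-controlled neuroimaging studies. The Design section makes each Aim sham-controlled and lists cue reactivity among the primary hypotheses. The power statement covers brain measures. Hypothesis wording proves little about the comparator: the behavioural hypotheses also say only that iTBS will lower the measures, and they are then analysed real versus sham. All of this stands. It establishes intent, but does not name a test, an ROI or a condition.

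A reader might go further and infer that the plan prescribes a before-after test in the active arm, or a rule of significant under real but not under sham, so that the mechanistic conclusion would not rest on randomisation. The documents do not support that. No section prescribes either procedure. The pilot figure for Study 4 does carry the caption "Data shown are within group contrasts Visit 1 vs Visit 6", but the caption also mentions a factorial design, the text describes the result as relative to a sham group, and a pilot display is not this trial's analysis plan. The percentages in step 5 therefore show possible misuse, not the plan's error rate.

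It is also fair to say that the power shortfall at 36 v 18 is small, and that the drop to 73% comes from the attrition arithmetic rather than from the missing contrast.

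**Conclusion.** The point holds as an under-specification of a primary outcome. No real-versus-sham test of ROI change is stated, and the one group comparison named for the ROI outcomes is between serial, non-randomised cohorts. Crediting TMS with a change shared with sham is possible, not certain; how likely depends on the size of any shared change, on which the documents are silent.

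For the randomised contrast at d=0.8 in change-score SDs, unadjusted and two-sided 5%, power is about 78% at 36 v 18 and about 73% at 32 v 16, against 80% stated. These figures depend on the SD scale and the scan-rescan correlation. Baseline adjustment would raise them and unscanned participants would lower them. Aim 2 has a further gap: the Objectives predict an increased response in the resist condition, while Hypothesis Aim 2 states both an increase and a decrease, so the direction under test is not settled.

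**What to change.** 1. **Reconcile the Aim 2 direction** between the Objectives and Hypothesis Aim 2, by region and condition, before writing the test.
2. **Name the primary imaging test** in the hypothesis paragraphs. Within each Aim, regress Visit 10 cigarette-minus-neutral percent signal change on arm (real or sham), with the Visit 1 value and the stratification factors as covariates (the follow-up paragraph mentions gender and depression). State the condition and one primary ROI, or keep the listed ROIs with a multiplicity correction. Extending the behavioural real/sham-by-time model to the ROI outcomes would also close the gap; baseline adjustment is suggested for its power.
3. **Label within-arm Visit 1 to Visit 10 contrasts as descriptive.**
4. **Make Aim 2 versus Aim 1 secondary**: a non-randomised comparison of the two real-minus-sham differences.
5. **Restate imaging power** in the Sample Size section for the 2:1 contrast at expected scan counts, giving the SD scale, the assumed correlation and an allowance for unscanned participants.

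The cost is a few sentences of analysis text and a slightly less favourable stated power. No extra scans, participants or data collection are needed.
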